- 6. the activity of secreted sphingomyelinase is suitable as a biomarker for alcohol consumption and prediction of medication effects
- 7. safety issues occur during the use of the investigational medicinal products

- 8. the administration of acamprosate or ionized calcium (Ca²⁺ = ready-to-use drug Calcium-Verla[®]) lowers threshold at which participants decide it is no longer worthwhile to work for an additional alcohol reward ("break point").
- 9. the administration of acamprosate or ionized calcium (Ca²⁺ = finished medicinal product Calcium-Verla®) reduces the maximum and mean blood alcohol concentration (BAC) in an alcohol self-administration experiment.
- 10. the administration of acamprosate or ionized calcium (Ca^{2+} = ready-to-use drug Calcium-Verla®) reduces the work for saline infusions as an alternative reinforcer.
- 11. the aforementioned points (1 to 3 and 8 to 10) differ in the first and second half of the experiment.
- 12. the acamprosate level in the group of subjects treated with acamprosate influences the primary outcome of the aforementioned points

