1.2 STUDY DESIGN

This is a monocentric study in a placebo-controlled, randomized design with three treatment groups. The administration of the investigational drugs is conducted in a double-blind manner with placebo, acamprosate, or calcium carbonate.

The comparison will be made between the calcium group and the placebo group, as well as between the acamprosate group and the placebo group.

Self-infusion of the NIMP (alcohol / saline solution) will be conducted openly regarding the preparation and single-blind regarding the dosage during visits alcohol self-administration visits V2 and V5.

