- 4. Alcohol craving in daily life will be measured using the "Obsessive Compulsive Drinking Scale" (OCDS, from obsessive [OCDSO], compulsive [OCDSK] and total score [OCDST]) before both self-administration experiments (V2 and V5) to compare treatment-related changes between the 3 treatment arms
- 5. Violations of the imposed abstinence are recorded as the proportion (%) of days with alcohol consumption detected (by TLFB) [VABST] to compare them between the three treatment arms and to investigate their influence on the primary endpoint.
- 6. Motivation to change drinking habits. The "Readiness to change" questionnaire is used to determine which of the three stages of change in drinking habits the participants are currently assigned to. Subscores of the Pre-Contemplation [RTCP], Contemplation [RTCC] and Action [RTCA] will be anlyzed. Differences between the stage of change before the study (screening), after completion of the study procedures (visit 6) and after completion of the brief intervention (telephone follow-up) will be considered independently of the treatment arm. The number of participants for whom the readiness to change increases, remains the same and decreases will be described.
- 7. Drinking habits will be assessedusing the Timeline follow-back interview (TLFB) at screening (or re-screening), at visits 1, 3 and 6 and at the telephone follow-up. Changes in drinking habits as a result of study participation will be recorded by comparing the drinking amounts during the 45 days prior to the start of the study (measured at the screening or re-screening) with those after the end of the study (telephone follow-up interview). The following points will be examined in each of the 3 treatment arms:
 - a) the percentage of drinking days [TFbITT],
 - b) the average amount drunk per drinking day [TFbIAVE],
 - c) the percentage of days with heavy alcohol consumption (over 60 g for men and 48 g for women = "binge days") [TFbIBT], and
 - d) the average amount of alcohol on these binge days [TFbITM]

- 8. Determine whether participants have ever received addiction treatment services [SSBNY] (e.g., addiction-specific counseling/treatment by an addiction counseling center or general practitioner or psychologist or psychiatric specialist or hospital) in comparison before study participation (for screening) and afterwards (visit 6 and telephone follow-up interview)

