6.5 SECONDARY ANALYSES

6.5.1 Efficacy

All parameters listed below will be examined descriptively in a first step and only analyzed using exploratory statistical methods if notable differences or discrepancies are observed. The aim of exploratory data analysis is to generate hypotheses as a basis for future research projects.

Secondary endpoints related to alcohol self-administration will include:

a. Difference between visit 2 and visit 5 of the "break points" in the "progressive work" scheme for working for alcohol. The "break point" represents the performance threshold at which participants decide it is no longer worth working for another reward (alcohol) and thus stop the CAT before reaching the next reward.

The comparison of the difference in break points between Visit 2 and Visit 5 among the three groups will be conducted descriptively using frequency tables, median, range, maximum, minimum, and appropriate graphical representation.

b. Difference in maximum and mean blood alcohol concentration (BAC) achieved during alcohol self-administration between visits 2 and 5.

This parameter will be analyzed using analyses of variance (ANOVAs).

c. Difference in the cumulative number of work trials for saline solution in the "constant attention task" between visit 2 and visit 5:"

The differences in the three groups will be compared using ANOVA.

d. Investigation of the primary and the above-mentioned secondary parameters of alcohol self-administration, considering only the first and second halves of the experiment. For this purpose, the cumulative number of work trials for alcohol and saline in the CAT will be recorded every 30 seconds during an experiment.

The analyses will be conducted according to the primary and the relevant secondary parameters of alcohol self-administration.

In addition, the following secondary questions will be investigated:

1. does the administration of acamprosate or calcium ions compared to placebo lead to altered subjective perception of alcohol effects?

The subjective perception of alcohol effects will be measured using visual analog scales ("quizzer") before, during and after the experiment at visits 2 and 5 in order to compare their alcohol-induced changes between the 3 treatment arms. The values and the "slopes" (changes) between two measurement points will be analyzed.

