Repeated measures ANOVA will be used for analysis, with primary and secondary endpoints of alcohol infusion as covariates. The relationship between alcohol infusion endpoints and subjective data will be further examined using correlation analyse.

2. can the efficacy of acamprosate or calcium ions be predicted by basal levels or changes over time in measures of body calcium reserves indicating possible calcium deficiency?

The blood levels of total calcium, phosphate, magnesium, albumin, parathyroid hormone, 25-hydroxyvitamin D will be measured at visit 2 and visit 5. Baseline values and the difference in values between V2 and V5 will be examined for their relation to the primary endpoint in the three treatment arms.

The relationship between body calcium reserves and efficacy will be investigated using correlation analyses and regression analyses. Group comparisons will be conducted using ANOVA.

3. does the administration of acamprosate or calcium ions reduce alcohol cravings in daily life?

Alcohol craving in daily life will be measured using the "Obsessive Compulsive Drinking Scale" (OCDS) before both self-administration experiments to compare treatment-related changes between the 3 treatment arms.

The change in the total OCDS score and the two subscores will be compared between the three groups using repeated measures ANOVAs.

4. does the frequency of reported alcohol consumption during the imposed abstinence period differ between treatment groups, and how does this affect the work for alcohol after the imposed abstinence period?

Violations of the imposed abstinence will be recorded as the percentage (%) of days with alcohol consumption reported (by TLFB) to compare them between the three treatment arms and to examine their influence on the primary outcome measure.

Group comparisons regarding the frequency of alcohol consumption will be performed using ANOVA. The influence on the primary endpoint will be examined using regression analysis and correlation analysis.

5. does participation in the study promote the motivation to change drinking habits or alter drinking habits or the utilization of addiction treatment services?

Motivation to change drinking habits:

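### Exploratory ANOVAs of change in craving, BAC and saline work leave out adjustment for the V2 value and do not specify the two contrasts with placebo

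*SAP*

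**What the plan says.** Section 6.5.1 sets the methods for the secondary efficacy endpoints:

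- Craving (OCDS total and the two subscores, measured before the V2 and V5 experiments): "The change in the total OCDS score and the two subscores will be compared between the three groups using repeated measures ANOVAs".
- Maximum and mean BAC, each taken as a V2-V5 difference: "This parameter will be analyzed using analyses of variance (ANOVAs". Nothing more is said about groups, covariates or contrasts.
- Work for saline, also a V2-V5 difference: "The differences in the three groups will be compared using ANOVA".

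For these endpoints the SAP names no V2 covariate, contrast with placebo, confidence interval or repeated-measures term to be tested.

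On which arms are compared, section 1.2 says: "The comparison will be made between the calcium group and the placebo group, as well as between the acamprosate group and the placebo group". Section 4.3.1 describes the craving endpoint differently; OCDS is measured "to compare treatment-related changes between the 3 treatment arms". The questions themselves are directional: craving, "does the administration of acamprosate or calcium ions reduce alcohol cravings in daily life"; BAC, whether the drug "reduces the maximum and mean blood alcohol concentration (BAC) in an alcohol self-administration experiment"; saline, whether it "reduces the work for saline infusions as an alternative reinforcer".

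Section 6.5.1 also says that these parameters are first described, and are tested with exploratory methods only where notable differences are seen.

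**The concern.** Section 1.1 describes V2 as the visit without medication. Section 6.3 stratifies randomisation on information up to V4, so V2 precedes randomisation. Each participant therefore has a true pre-treatment value of the same measure. A change score uses that value with its coefficient fixed at 1; ANCOVA estimates the coefficient and usually leaves less residual variance. The planned analyses forgo that gain although the data are already collected.

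The second matter is what gets reported. An overall F-test across three arms has two degrees of freedom and no direction. It does not say which arm differs from placebo, or by how much. The questions ask whether a drug reduces something, and section 1.2 makes placebo the reference. For BAC, section 1.1 goes further and sets a placebo-referenced benchmark: a reduction of at least 0.1 per mille between V2 and V5 relative to placebo. An F-test gives no estimate to set against it. Section 6.5.1 gives the purpose of these analyses as generating hypotheses for future research, and for that an estimate with an interval is more useful than an F-test.

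**Working it through.** **Inputs.** From the SAP: one unmedicated value (V2) and one on-treatment value (V5) per participant, in three arms. Not in the SAP: the V2-V5 correlation rho, the two standard deviations, and any precision or power figure for these endpoints. There is thus no planned figure to reproduce; rho is assumed over a range.

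**Step 1: the repeated-measures ANOVA is a change-score test.** With two visits, a participant's within-subject part is plus and minus half the change. The group-by-time sum of squares is therefore half the between-group sum of squares of the change, and its error term is half the within-group sum of squares of the change. The halves cancel, leaving the same F on 2 and N-3 degrees of freedom. A simulated data set confirmed this: F = 1.668 for the group-by-time term and F = 1.668 for one-way ANOVA on the change. The group main effect is a different test (F = 0.644 in the same data), because it averages in the unmedicated visit.

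**Step 2: precision.** Assume equal V2 and V5 variances, scaled to 1.

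- Change-score residual variance: 2(1 - rho)
- ANCOVA residual variance: 1 - rho²
- Ratio, ANCOVA to change score: (1 - rho²) / [2(1 - rho)] = (1 + rho)/2

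| Assumed rho | Change score | ANCOVA | Ratio | Less variance with ANCOVA |
|---|---|---|---|---|
| 0.3 | 1.40 | 0.91 | 0.65 | 35% |
| 0.5 | 1.00 | 0.75 | 0.75 | 25% |
| 0.7 | 0.60 | 0.51 | 0.85 | 15% |
| 0.9 | 0.20 | 0.19 | 0.95 | 5% |

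**Step 3: without equal variances.** Let s1 and s2 be the V2 and V5 standard deviations.

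- Change score: s1² + s2² - 2·rho·s1·s2
- ANCOVA: s2²(1 - rho²)
- Excess of the change score: s1² - 2·rho·s1·s2 + rho²·s2² = (s1 - rho·s2)²

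The excess is never negative, and it is zero only when rho = s1/s2. The direction therefore does not depend on equal variances, but the percentages in the table do.

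**Step 4: what the overall F-test costs.** For illustration only, assume 30 per arm, one active arm differing by 0.6 SD, the other active arm equal to placebo, rho 0.5 and two-sided 0.05. Power is 65% for the overall F-test on change, 63% for the change-score contrast with placebo and 76% for the ANCOVA contrast with placebo. In this case the loss comes from leaving out the baseline adjustment; the overall test itself costs no power. Its weakness is that it gives neither direction nor a difference from placebo.

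**The case against.** The strongest reply is that this is a choice of method for exploratory endpoints, and that the plan is not wrong. Much of it stands. Change-score analysis is unbiased under randomisation and matches the BAC and saline endpoints, which section 4.3.1 defines as V2-V5 differences. The tests run only after description by arm, so a reader would already see whether a significant F reflected acamprosate against calcium.

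Several stronger readings are tempting, and the document does not support them:

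- A reader might infer that the plan fails to answer its own stated comparisons. For craving, sections 4.3.1 and 6.5.1 themselves call for a comparison among three arms, and the objectives on craving, BAC and saline work name no comparator. An ANOVA can also carry contrasts with placebo; the SAP leaves them unspecified but does not exclude them. The fault is loose alignment with section 1.2.
- A reader might infer that craving will be judged on the group main effect, which dilutes the drug effect. The SAP says that the change is compared, which points to the group-by-time term. Not naming the term is a small gap in wording.
- A reader might say that V2 is ignored. A change score does use it; what is missing is an estimated coefficient.
- A reader might take the BAC analysis as stated to be three-group. That is likely, but the BAC sentence does not say so.

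None of this removes the point that a more precise analysis, reporting the comparisons named in section 1.2, is available from data already collected.

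**Conclusion.** The point holds as an optional improvement. For OCDS total and subscores, maximum and mean BAC, and work for saline, the SAP plans unadjusted analyses of change and does not specify the two contrasts with placebo. The plan is valid but generally less precise than it could be. The likely saving in variance runs from 35% at a correlation of 0.3 to 5% at 0.9, assuming equal V2 and V5 variances. Neither the correlation nor the variances can be fixed from the SAP, and the gain is small if the two visits are highly correlated.

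A reader might infer that the trial's main result is weakened. It is not: the confirmatory tests in section 6.4 are separate, already compare each drug with placebo, and do not depend on these analyses.

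**What to change.** In section 6.5.1, for OCDS total and both subscores, BACMAX, BACMEAN and CATWAT, specify ANCOVA of the V5 value on treatment arm and the V2 value of the same measure, together with the two stratification factors of section 6.3 (severity of addiction characteristics; wish to reduce consumption). Report the acamprosate-placebo and calcium-placebo differences with 95% confidence intervals, in addition to or in place of the overall F-test. Align the craving wording in sections 4.3.1 and 6.5.1 with the comparisons in section 1.2. If repeated-measures ANOVA is kept for OCDS, name the group-by-time term as the test of interest.

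The analyses by half of the experiment (section 6.5.1, item d) follow the methods of the corresponding endpoints, so for BAC and saline work they would take over the change.

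The cost is SAP wording only. All values are already collected, and neither the sample size nor the confirmatory analysis changes.

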6.5.2 Safety / tolerability

The CIWA-Ar score will be categorized (mild/moderate/severe) and compared between the treatment groups using a cross-tabulation and chi-square test.

Blood pressure and pulse values will be are documented at screening and visits 1 to 6 and compared using appropriate methods.

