2.4 SAFETY PARAMETERS

The safety parameters will be analyzed using the Safety Analysis Set. This population comprises all subjects who have at least started the administration of an investigational product (including placebo lead-in). The subjects are assigned to the treatment group according to treatment they actually received (analysis "as treated").

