4.3.2 Endpoints related to safety/tolerability during the treatment period

- 1. Occurrence of adverse events from visit V1 to V6 [SAESEQ]
- 2. CIWA-Ar-Score, values for blood pressure and pulse for screening and visits 1 to 6 [CIWA].

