6.3 EXPOSURE TO THERAPY AND COMPLIANCE

Randomization will be stratified according to the two criteria:

- a) Severity of addiction characteristics up to the time of V4
 - "High" if there is at least a moderate alcohol use disorder according to DSM-5, i.e., the presence of at least 4 of the 11 criteria, or if significant physical alcohol withdrawal symptoms were reported anamnestically or observed by study physicians (CIWA at V3 or V4 > 6 points).
 - "Low" if there is only a mild alcohol use disorder according to DSM-5, i.e., the presence of no more than 3 of the 11 criteria, and physical withdrawal symptoms were neither reported anamnestically nor observed by physicians..

b) Answer to the question at time V4 as to whether patients want to reduce their alcohol consumption ("yes" or "no")

This stratification aims to ensure that the distribution of these two characteristics does not differ between the three treatment arms before the start of treatment.

It is hypothesized that acamprosate will have a more pronounced effect the more severe the addiction-related pathological changes in the reward system are. This aspect is captured by the composite factor "Severity of Addiction Characteristics" (criterion a).

Since the overwhelming majority of acamprosate studies in humans only included patients who wanted to reduce or stop their alcohol consumption, the clinical efficacy insights of acamprosate are limited to this group. On the other hand, it seems

inappropriate to make the desire for reduction a prerequisite for participation, as based on animal experiments and the observations of Mason et al. (2006), acamprosate reduces alcohol consumption even when there is no explicit desire for change, especially under the specific conditions of prior enforced abstinence.

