6.4 CONFIRMATORY ANALYSIS

Testing the two primary hypotheses

- H1: The administration of acamprosate compared to placebo leads to a significant reduction in the willingness to perform work in the laboratory experiment to obtain alcohol
- H2: The administration of calcium ions compared to placebo leads to a significant reduction in the willingness to perform work in the laboratory experiment to obtain alcohol infusions

Will be conducted using t-tests if the data is normally distributed. The test for normal distribution will be assessed using the Shapiro Wilk test and a graphical inspection of the distribution in the histogram. If the data is not normally distributed, Mann-Whitney tests will be used. The significance level is 0.025, as two null hypotheses are tested in the confirmatory analysis.

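### The CIWA-Ar comparison uses an unordered chi-square test on ordered classes, without a post-randomisation value or the subject's own pre-drug score; if scores are mostly low, a rise in withdrawal symptoms could be missed

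*SAP*

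**What the plan says.** Section 6.5.2 fixes the whole CIWA-Ar analysis in one sentence: "The CIWA-Ar score will be categorized (mild/moderate/severe) and compared between the treatment groups using a cross-tabulation and chi-square test". Section 4.3.2 lists what is collected: "CIWA-Ar-Score, values for blood pressure and pulse for screening and visits 1 to 6". That is up to seven scores per subject. Section 1.2 sets out the arms: "This is a monocentric study in a placebo-controlled, randomized design with three treatment groups".

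The only CIWA threshold in the SAP is in section 6.3, where it helps to define the high-severity randomisation stratum: "observed by study physicians (CIWA at V3 or V4 > 6 points". The low stratum covers mild disorder in which "physical withdrawal symptoms were neither reported anamnestically nor observed by physicians". The SAP gives neither the share of subjects expected in each stratum nor a CIWA distribution.

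Safety is analysed as treated (section 2.4), in "all subjects who have at least started the administration of an investigational product (including placebo lead-in".

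**The concern.** CIWA-Ar is a numeric score, and mild, moderate and severe are ordered classes of it. A Pearson chi-square test gives the same p-value however the classes are arranged, so it spreads its power over patterns that have no meaning as worsening. The SAP treats a comparable measure differently: for the three stages of readiness to change, section 6.5.1 plans a signed-rank test and ordinal logistic regression.

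The second weakness is timing. Section 6.5.2 does not say that only scores under randomised drug enter the table, and it makes no use of the subject's earlier score. Pre-drug CIWA is part of the stratification, so the SAP itself regards it as informative.

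The third is sparse cells. The adverse-event chi-square test in section 6.5.3 is to be run only where applicable; the CIWA test carries no such condition.

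At stake is the report of withdrawal symptoms by arm. A finding of no difference could reflect the coding and the test rather than the data.

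**Working it through.** **Timing, from the SAP alone.** The V4 score helps to assign the stratum (section 6.3), so it is known before randomised treatment starts. Section 1.1 places V2 without medication and V5 after administration. Screening and V1 to V4 therefore give 5 pre-drug scores, and V5 and V6 give 2 later ones. Only 2 of the 7 listed scores can show a drug effect.

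**Degrees of freedom.** Three arms by three classes give (3 − 1) × (3 − 1) = 4 for the unordered chi-square test. A Kruskal-Wallis test on the ordered classes has 3 − 1 = 2. For one active arm against placebo the figures are 2 and 1.

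**Simulation inputs.** The SAP has no figure to reproduce here. All of the following are assumptions: 30 per arm; three arms with one shifted; negative-binomial scores with shape 1 or 2; class limits at 8 and 16; two-sided 0.05; 1,500 runs per setting.

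**Sparse cells.** The expected number per arm in moderate and severe together is n × (sum of the three arms' probabilities) / 3. With shape 2:

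- means 1 vs 2: 30 × (0.001 + 0.001 + 0.020) / 3 = 0.22
- means 1.5 vs 3: 30 × (0.006 + 0.006 + 0.071) / 3 = 0.83
- means 3 vs 6: 30 × (0.071 + 0.071 + 0.300) / 3 = 4.42
- means 6 vs 10: 30 × (0.300 + 0.300 + 0.543) / 3 = 11.43

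The first three fall below the usual minimum of 5 even before severe is split off. At means 1 vs 2, every subject is in the lowest class in 26 to 50% of runs, so no test is possible. With no difference between arms (all means 1, shape 2), the chi-square test rejects in 0.000 of runs and the rank test on the score in 0.051.

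**Power for a general shift in one arm** (range over the two shapes):

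| Means | Chi-square on classes | Kruskal-Wallis on score |
|---|---|---|
| 1 vs 2 | 0.02–0.08 | 0.43–0.62 |
| 1.5 vs 3 | 0.23–0.25 | 0.48–0.69 |
| 3 vs 6 | 0.43–0.60 | 0.56–0.83 |
| 6 vs 10 | 0.32–0.52 | 0.35–0.62 |
| 10 vs 15 | 0.17–0.34 | 0.24–0.46 |

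At 6 vs 10 the gap is 0.351 − 0.319 = 0.03 to 0.623 − 0.517 = 0.11. At 10 vs 15 it is 0.237 − 0.170 = 0.07 to 0.457 − 0.335 = 0.12.

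**Power when a subgroup of one arm develops scores of 9 to 21** (base mean 1 to 2, 30 per arm):

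| Affected | Chi-square on classes | Kruskal-Wallis on score | Kruskal-Wallis on ordered classes |
|---|---|---|---|
| 10% | 0.17–0.25 | 0.08–0.10 | 0.27–0.57 |
| 20% | 0.58–0.76 | 0.26–0.29 | 0.70–0.94 |
| 30% | 0.88–0.97 | 0.53–0.57 | 0.92–1.00 |

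Here the ranking of the first two tests reverses, and the order-respecting test on the same classes is best.

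**Two-arm check of a general shift** (40 per arm, means 1.5 vs 3): 0.27 for chi-square, 0.38 for an order-respecting test on the classes, 0.60 for the rank test on the score.

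**The case against.** The low-score premise is an inference. Section 6.3 foresees a high stratum as well as a low one and gives no shares, and with higher scores the loss from using classes is modest. A reader might infer that the coding discards nearly all the information and that a withdrawal signal would be missed. The SAP does not support that: it states no score distribution, and clear withdrawal in a subgroup would appear in the cross-tabulation and is detected better by the classes than by a rank test on the score. This part of the objection stands, and it also rules out a rank test on the score as the sole replacement.

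A reader might also infer that section 6.5.2 contradicts the cut-off of more than 6 points. It does not. That cut-off assigns strata; the SAP does not present it as a safety threshold.

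The consequence is limited too. CIWA-Ar is a secondary safety measure, and the 0.025 level covers only the two primary hypotheses: "The significance level is 0.025, as two null hypotheses are tested in the confirmatory analysis". Adverse events, pulse and blood pressure are compared as well. This bears on severity, not on whether the test is well chosen.

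Finally, the heading of section 4.3.2 refers to the treatment period, which might be read as limiting the scores. The same item lists screening, so the heading does not settle the point.

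**Conclusion.** The point holds as a minor one. From the text alone, the planned test ignores class order and the pre-drug score and is not limited to scores after the first randomised dose. That the table will be sparse and that a rise could be missed depends on scores being mostly low, which is plausible given the low stratum but not documented.

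The power loss depends on score distribution, class limits and arm size, none of which the SAP states. Under the assumptions shown it is large for a general shift at low scores (0.02–0.08 against 0.43–0.62) and much smaller at higher ones (0.03–0.12). An order-respecting test on the same classes improved on chi-square in the subgroup settings and in the two-arm check. It has a limit: when only two classes are occupied, order adds nothing, so a shift within the lowest class can be seen only in the raw scores. The simulated tests were unadjusted and not exact; the gain from adjusting for V4 was not estimated.

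**What to change.** Replace the CIWA-Ar sentence in section 6.5.2 along these lines:

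- **Value:** one per subject, the highest CIWA-Ar score after the first randomised dose. Count separately those in the Safety Analysis Set who received only the lead-in or have no later score.
- **Comparison:** each active arm against placebo by a proportional-odds model adjusted for the V4 score. When cells are sparse, use an exact trend test on the ordered classes. Either takes the place of the unordered chi-square test.
- **Description:** the raw score by arm and visit, the number of subjects above 6 points (the SAP's own stratification cut-off, used here only to describe), and the mild/moderate/severe cross-tabulation without a test.

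The cost is SAP wording and one extra model, with no new data. The model brings the proportional-odds assumption. The exact test gives a valid p-value in sparse tables but does not restore power, which is why the raw-score description is needed.
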